The effect of lipid emulsions on free fatty acids and free bilirubin in premature newborns

NCT03857646

Version Date: 09/25/2019

Title: The effect of lipid emulsions on free fatty acids and free bilirubin in premature newborns

Background:

Recently published reports have renewed concerns that that lipid infusions might decrease bilirubin binding capacity (BBC) via competition for albumin binding sites from free fatty acids (FFA) such that free bilirubin (Bf) might rise to dangerous levels, particularly in newborns delivered at <28 weeks gestational age.^{1,2} Most recently, Hegyi showed elevated levels of unbound free fatty acid (FFAu) and free (unbound) bilirubin (Bf) with lipid infusion rates ≥ 2.5 g/kg/day, while previously Amin showed that a similar dose response measuring total free fatty acids (FFAt), which is almost entirely bound to albumin.^{1,3}

To date, the associations of lipid emulsions, FFA, and Bf, have only been studied with one soy-based lipid emulsion product, Intralipid. Soy based lipid emulsions are associated with cholestatic liver injury, particularly in premature newborns.³ However, there is evidence that a newer lipid formulation based on a mixture of soy, medium chain triglycerides, olive oil and fish oil (SMOF), causes less liver injury.^{4,5} It is believed that SMOF is more tolerable to the liver because of the reduced phytosterol components.¹ To date, neither FFA or Bf levels have been measured with SMOF or concurrently compared to levels with Intralipid. However, there is evidence that plasma triglyceride and other fat levels are higher with SMOF than Intralipid. D'Ascenzo conducted a small randomized trial comparing IL and SMOF in newborns infusing at 3.5g/kg/day and found that triglyceride (TG) levels were 39% higher in patients receiving with SMOF versus IL (231 vs 166 mg/dl).⁶ Although FFA levels were not measured in the D'Ascenzo study, a previous study in premature newborns receiving Intralipid reported a strong positive correlation ($r = 0.89$, $P < 0.001$) between triglyceride and FFA levels.⁷

The primary research question for the present study is whether the observed difference in TG levels with IL versus SMOF might also be associated with a difference in FFA and Bf levels. Based on previous reports of higher triglyceride levels with SMOF versus Intralipid and a positive correlation between triglyceride and FFA levels, FFAu levels would be expected to be higher with SMOF than Intralipid. However, it is possible that the triglyceride – FFA correlation observed with Intralipid may not be observed with SMOF. In any case, clinicians should know whether FFA and Bf levels are increased, decreased, or equivalent with SMOF versus IL.

Hypothesis:

At a dose of 3 g/kg/day, patients receiving Intralipid will have lower mean concentrations of free bilirubin (primary outcome) and free fatty acids (secondary outcome) than patients receiving SMOF.

Study Population: 64 Premature newborns (<32 weeks gestation, stratified <28 weeks versus ≥ 28 weeks) <8 days of age and receiving lipid infusions ≤ 1 g/kg/day at enrollment and anticipated to be treated with 3 g/kg/day for a minimum of 48 hours.

Patients with direct hyperbilirubinemia > 1.8 mg/dl, with suspected sepsis meeting SIRS criteria, undergoing treatment with a continuous infusion of morphine or positive blood cultures at the time of enrollment will be ineligible to enroll in the study. Patients on continuous infusion of pressors (dopamine, dobutamine, epinephrine, etc.) will be ineligible to enroll in the study if they have single lumen central access; patients with multiple lumen access will not be excluded.

Study Design: Randomized controlled trial, Intralipid versus SMOF lipid emulsion

Primary outcome measures:

- Bf serum levels during lipid infusion at 3 g/kg/day (first and second day of infusions at 3 g/kg/day)

Secondary outcomes:

- FFAu serum levels during lipid infusion at 3 g/kg/day (first and second day of infusions at 3 g/kg/day)

- FFA at serum levels during lipid infusion at 3 g/kg/day (second day of infusion at 3 g/kg/day)
- Direct bilirubin, proportion with peak >1.8 mg/dl
- Serum triglyceride level, mean and proportion with peak value >350 mg/dl
- Evaluation of growth at 28 days of life

Methods

Patients for whom informed consent has been obtained will be randomized to IL or SMOF using REDCap software. Treatment allocation per randomization (IL versus SMOF) will remain in effect through the intervention period: until the 2nd blood sample at 3 g/kg/day or 2 weeks of age, whichever comes first. Clinicians cannot be masked to the lipid emulsion – see safety precautions, below

Blood samples for the study will be obtained with blood draws for clinical measurement of bilirubin and/or triglyceride levels such that the study will not require additional interventions for blood sampling – see blood sampling schema below. When treated with 3 g/kg/day, blood will not be sampled if patients have received a mixture of SMOF and IL in the preceding 24 hours, or if SMOF or IL infusions were interrupted for ≥ 2 hours in the preceding 24 hours. Daily weights and serum bilirubin and triglyceride levels will be abstracted from the medical record.

This study will also include measurements that were not included in previous studies in order to validate measures and obtain a fuller picture cause and effect mechanisms. These measures include serum albumin, bilirubin binding capacity, reserve bilirubin binding capacity, and 2 methods for measuring free fatty acid – both bound and unbound free fatty acids. Serum for FFAu and Bf and albumin, will be stored at -80 C and shipped to Fluoresprobe Sciences.^{8,9} Bilirubin binding capacity (BBC) and related measures will be measured with hematofluorometry within 12 hours of sampling.^{10,11} Total FFA will be measured at UT Houston SOM.

Per usual care, lipids start at 1 g/kg/day and advance by 1 g/kg/day to a max of 3 g/kg/day as tolerated by the neonate. Blood samples will be collected when lipids are at the following amounts as listed below:

Blood Sampling Schema:

Lipid Dose (g/kg)	Total sample in (mL)
1	0.5
2	0.5
3	0.5
3	0.5
Total	2.0

Two samples will be obtained with the lipid emulsion at 3 g/kg/day in order to follow these values in a steady state at the maximum dosage.

Safety Precautions:

During the intervention period (until the 2nd blood sample at 3 g/kg/day or 2 weeks of age, whichever comes first), the lipid emulsion may be changed without violating the study protocol so long as the change follows usual standard of care practice. Subject to change in NICU guidelines, IL will be discontinued or changed to SMOF if direct bilirubin level is ≥ 2.0 mg/dl, and SMOF will be changed to IL while potentially incompatible medications are infusing via the same intravenous line. This means that both lipid emulsion infusions will be managed following usual standard of care practice (i.e., in the same way as in patients not enrolled in the study). After the intervention period, lipid emulsion may be changed at the discretion of the attending physician.

Data Analysis: Mean values will be compared using Student's t test, over all patients and within gestational age strata. Proportions will be compared using the chi square test. Dose responses will be analyzed and compared using multilevel regression to account for repeated measures within patients. Point estimates and 95% confidence levels will be reported for all outcomes.

Data Management: Data will be entered and stored in a secure University of Texas Health Sciences REDCap database.

Power and Sample Size:

[figure not shown]
Based on the sample size calculation below, a feasible sample size of 64 patients (32 in 2 groups) would result in power of 0.81 with alpha at 0.05 to detect an 39% difference in mean Bf levels, SMOF versus IL infusing at 3 g/kg/day.

D'Ascenzo conducted a small randomized trial comparing IL and SMOF in newborns and infusion at 3.5g/kg/day and found that triglyceride (TG) levels were 39% higher with SMOF versus IL in patients receiving 3.5 g/kg/day (table below).⁷

Table	Intralipid	SMOF	delta	delta %
Triglyceride) mean +SD	166 +47 mg/dl	231 +59 mg/dl	65 mg/dl	39 %
Triglyceride levels Intralipid vs SMOF at 3.5 g/kg/day (D'Ascenzo et al)				

Absent other relevant data, we hypothesize that mean FFAu and mean Bf levels will also be 39% higher with SMOF versus IL (day 2 at 3 g/kg/day). Hegyi reported FFAu of 67 ± 173 and Bf levels of 15.9 ± 8.5 (mean,SD) with IL infusions of 3 g/kg/day (figure 1). For reasons of feasibility but also because Bf levels are clinically more important, we based sample size and power calculations on Bf rather than FFAu.

Figure Effects of increasing intralipid dose from 0 to 3 g/kg/d (Hegyi et al)

Given Bf levels (nM) of 15.9 ± 8.5 with IL versus 22.1 ± 8.5 with SMOF (delta = 39%), a sample size of 62 patients (31 in 2 groups) will result in power of 0.81 with alpha at 0.05. Likewise, power will be 0.81 to detect an 39% decrease (SMOF 9.7 ± 8.5).

Observational Outcomes :

Evaluation hematofluorometry's capacity to detect displacement of bilirubin from albumin by free fatty acids and of the correlation of Bf and the saturation index.

Unrelated to comparisons between Intralipid and SMOF, a number of analyses will address important questions. Hematofluorometry is the methodology employed to measure bilirubin binding capacity (BBC). With total serum bilirubin (TSB) and Bf, BBC is one of three measured components in the bilirubin binding panel proposed by Ahlfors.^{10 11 12} Calculated components of the bilirubin binding panel include reserve bilirubin binding capacity (RBBC), calculated as the difference between BBC and bound bilirubin, and the bilirubin-albumin equilibrium dissociation constant (Kd). The clinical problem of unrecognized high Bf levels secondary to FFAs displacing bilirubin from albumin is a prime example of the potential utility of the bilirubin binding panel, and the limitations of relying on TSB alone. The question arises: should clinicians also measure BBC and Bf, and perhaps FFA, as they prescribe lipid emulsion during the first weeks after birth? The value of including BBC and RBBC in the bilirubin binding panel in addition to Bf is that the former measures should be give an earlier and more reliable danger signal. This is because Bf levels remain relatively stable until binding capacity is reached, then rises quadratically – such that the danger signal may only be appreciated too late. However, the capacity of hematofluorometry to detect FFAs effect on BBC in the clinical setting is uncertain. Specifically, there is a step in the measurement method that could, in theory, displace FFA from albumin such that the *in-vivo* effect on RBBC might be underestimated. In the current study, we can test the capacity of hematofluorometry to detect the effect of FFA on BBC in the following manor. To the extent that elevated Bf levels are caused by FFAs displacing bilirubin from albumin binding sites, measured BBC should decrease as Bf levels rise. It is believed that this phenomenon becomes when the molar ratios of FFA to albumin exceed ~4:1 (Amin, Maisels, Watchko, 2017).² However, it is necessary to measure and adjust for concurrent changes in albumin concentrations because this also affects both Bf and BBC.

The hematofluorometry saturation index, calculated as bound bilirubin divided by RBBC, provides a second means by which the capacity of hematofluorometry to detect displacement of bilirubin from albumin by FFAs can be evaluated. The saturation index (SI) has been reported to have a tight correlation with Bf (figure 2).¹³ However, the correlation is dependent on accurate measurement of BBC and RBBC. Finding that the correlation of SI and Bf persists at high Bf levels despite high FFA levels would provide evidence that BBC and RBBC are measured accurately under these conditions. Conversely, finding that SI-Bf correlation deteriorates as FFA and Bf levels rise would provide evidence that hematofluorometry may not be suitable for guiding decisions regarding phototherapy and lipid infusions for premature newborns. It is acknowledged that these analyses are dependent on observing adequate variation in FFA and Bf levels, and that FFA reach levels that are high enough to displace bilirubin from albumin – all of which have been observed in previous similar studies.¹

[figure not shown]

Fig. 1. A plot of the apparent unbound bilirubin concentration as determined by the “peroxidase” method (U) vs the ratio of albumin-bound bilirubin to reserve bilirubin binding capacity as determined with the hematofluorometer (B/R) for a series of specimens prepared by addition of bilirubin to blood obtained from a single adult donor

Figure 2

References

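### The no-mixture rule covers only the 3 g/kg/day samples, and the dose-response comparison has no rule for 1 and 2 g/kg/day samples taken on pre-assignment or non-assigned emulsion

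*Combined protocol and SAP*

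**What the plan says.** **Samples.** Methods plans four study samples per infant: one at 1 g/kg/day, one at 2 and two at 3 ("Blood samples will be collected when lipids are at the following amounts as listed below").

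**Exclusion rule.** The same section says "When treated with 3 g/kg/day, blood will not be sampled if patients have received a mixture of SMOF and IL" within the previous 24 hours, and the sentence goes on: "or if SMOF or IL infusions were interrupted for ≥ 2 hours in the preceding 24 hours". Both conditions hang on the opening clause about 3 g/kg/day. No counterpart is given for the two lower doses.

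**Entry.** Study Population admits infants "receiving lipid infusions ≤ 1 g/kg/day at enrollment". It does not say which product they are on. Methods adds that usual care begins lipids at 1 g/kg/day.

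**Switching.** Methods says the allocation holds through the intervention period, but Safety Precautions says that in this period "the lipid emulsion may be changed without violating the study protocol so long as the change follows usual standard of care practice". It describes changes in both directions: "IL will be discontinued or changed to SMOF if direct bilirubin level is ≥ 2.0 mg/dl", and SMOF gives way to IL while possibly incompatible drugs share the line. Neither is tied to a dose.

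**Analysis.** Data Analysis states: "Dose responses will be analyzed and compared using multilevel regression", allowing for repeated measures within infants. It names no analysis population and no term for the emulsion received, and does not say how a sample on mixed or non-assigned emulsion is handled.

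**The concern.** The comparison of dose responses between arms uses samples at all doses, but exposure is screened at only one of them. An infant on one product at entry and randomized to the other can contribute a 1 g/kg/day sample that partly or wholly reflects the first product. Study samples are drawn alongside clinical blood draws, so the study does not time them to follow a period on the assigned emulsion. Later switches can have the same effect at 1 or 2 g/kg/day.

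Uneven screening matters for a slope. If contamination were equal at every dose, the arm difference would shrink in proportion throughout. If it is heavier at low doses, the difference is reduced at one end of the dose range more than at the other, and the fitted slope difference changes for reasons unrelated to how the two emulsions behave. The usual reassurance that contamination only pulls towards no difference does not carry over. At stake is a statement that the arms do, or do not, diverge as dose rises.

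**Working it through.** **The plan's own figure.** Power and Sample Size gives Bf of 15.9 versus 22.1 nM, SD 8.5, 31 per group, alpha 0.05 and power 0.81. The difference is 22.1 − 15.9 = 6.2 nM, and 6.2/15.9 = 39%. The noncentrality is 6.2 / (8.5 × √(2/31)) = 2.87 on 60 degrees of freedom. A two-sided t test then has power 0.807 (0.819 with 32 per group). The stated figure reproduces, and this point does not dispute it.

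**Inputs for the slope.** From the documents: sampling doses 1, 2, 3, 3, and a hypothesized difference of 6.2 nM at 3 g/kg/day. Assumed, because the documents give neither: the true difference at lower doses, and the off-assignment shares.

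**Formulas.** Let s be the sum of the off-assignment shares in the two arms at a given dose, with each sample behaving as the emulsion actually received. Then

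observed difference = true difference × (1 − s).

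The doses have mean 2.25, deviations −1.25, −0.25, 0.75, 0.75, and sum of squares 2.75. The least-squares slope of the arm difference on dose is

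slope = Σ(deviation × observed difference) / 2.75.

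**True difference proportional to dose.** The true slope difference is 6.2/3 = 2.07 nM per g/kg/day, so the differences at the four samples are 2.07, 4.13, 6.2 and 6.2.

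- Shares 50% at dose 1, 25% at dose 2, none at dose 3: observed 1.03, 3.10, 6.2, 6.2. Slope = (−1.29 − 0.775 + 9.30)/2.75 = **2.63**, or 27% too high.
- The same, plus 20% at both dose-3 samples: observed 1.03, 3.10, 4.96, 4.96. Slope = (−1.29 − 0.775 + 7.44)/2.75 = **1.95**, about 5% too low.
- 20% at every dose: 0.8 × 2.07 = **1.65**, 20% too low.
- Milder low-dose shares, dose 3 clean: 10% of SMOF-arm samples on IL at doses 1 and 2 gives 2.20 (6% too high); 30% crossed over in both arms gives 2.86 (38% too high).

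**Arms differ only at 3 g/kg/day.** True differences are 0, 0, 6.2 and 6.2. Slope = 9.30/2.75 = **3.38** whatever the shares at doses 1 and 2, because there is no low-dose difference to shrink. Low-dose contamination causes no bias.

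The plan gives no within-infant correlation, so these shifts cannot be set against the standard error of the slope.

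**The case against.** A reader might infer that the rule builds a false divergence into the trial. With a constant difference of 6.2 nM at every dose, the true slope difference is zero, yet shares of 25% or 50% at dose 1, or 50% and 25% at doses 1 and 2, give 0.70, 1.41 or 1.55 nM per g/kg/day. The documents do not support that premise. Power and Sample Size hypothesizes the 39% difference on the second day at 3 g/kg/day. Background reports raised Bf at infusion rates of 2.5 g/kg/day or more. The section on observational outcomes says Bf stays fairly stable until binding capacity is reached. On that account the low-dose difference may be small.

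Nor is inflation assured. The rule bars a mixture in the past 24 hours, but not a complete switch made before that, so the 3 g/kg/day samples may not be clean. As shown above, a modest share there reverses the direction.

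A reader might also infer that mixed samples will be counted under the assigned arm. The plan does not say so; it leaves their handling open. It is likewise not stated which product infants receive before enrolment, or whether any 1 g/kg/day sample precedes the assigned emulsion.

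An analysis strictly by assigned arm could be defended as treating switches as part of the strategy. That has force for switches after treatment starts. But the plan names no such estimand, and dropping mixed samples at 3 g/kg/day alone does not fit it. A sample drawn before the assigned emulsion starts carries no treatment effect under any estimand.

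Lastly, the comparison is in neither outcome list and no power is claimed for it. That is fair, and it limits the weight of the point.

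**Conclusion.** The gap is real and its reach is limited. The rule as worded does not cover the 1 and 2 g/kg/day samples, entry and switching provisions allow off-assignment exposure at those doses, and the multilevel comparison has no rule for it. Where the arms truly differ at low doses, the slope comparison can be distorted.

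No single size or direction can be stated. Under a difference proportional to dose, the assumed shares move 2.07 to 2.63, or to 1.95 once 20% of exposure at 3 g/kg/day is also off assignment. If the arms differ only at 3 g/kg/day, or if no infant starts on or switches to the other product, low-dose exposure causes no bias.

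A reader might infer that the main result is compromised. It is not affected by this gap: Bf as primary outcome, and FFAu and FFA as secondary outcomes, are all defined at 3 g/kg/day. The point bears on the dose-response comparison alone.

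**What to change.** 1. Record the emulsion given in the 24 hours before every study sample, at all doses.
2. In the dose-response model, code samples drawn before the assigned emulsion starts as pre-assignment, with one common mean for both arms.
3. Keep all later samples by assigned arm as the main analysis.
4. Add a sensitivity analysis that admits 1 and 2 g/kg/day samples only after 24 hours of the assigned emulsion alone, and state that this restriction is selection after randomization.

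The restricted analysis should not be the main one. It keeps infants randomized to the product they already receive and drops those randomized to the other, so it may remove points mostly from one arm. Later switches depend on direct bilirubin or co-medication, which adds further selection.

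The cost is one data field, a few sentences of analysis text, and fewer arm-specific points at 1 g/kg/day. No extra blood or patients are needed, and no clinical switching rule changes.

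### Infants are stratified at 28 weeks, but the overall free bilirubin comparison leaves the stratum out and loses some precision if levels differ by gestational age

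*Combined protocol and SAP*

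**What the plan says.** Study Population describes the infants as "stratified <28 weeks versus ≥ 28 weeks". Methods says that they "will be randomized to IL or SMOF using REDCap software"; that sentence names no strata or blocks. Data Analysis compares means by Student's "t test, over all patients and within gestational age strata". The only model in the plan is for another purpose: "Dose responses will be analyzed and compared using multilevel regression to account for repeated measures within patients". No gestational-age term is named for it. Data Analysis also commits to intervals: "Point estimates and 95% confidence levels will be reported for all outcomes".

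The Hypothesis concerns an overall difference in mean Bf between the emulsions and says nothing about a different effect by gestational age. Power and Sample Size assumes Bf (nM) of "15.9 ± 8.5 with IL versus 22.1 ± 8.5 with SMOF" and treats the trial as a plain two-group comparison.

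**The concern.** When allocation is balanced within strata, the difference in arm means no longer contains the between-stratum variation, because each arm has the same mix of infants. A two-sample t test still counts that variation in its standard error. The point estimate is the same, but the interval is too wide and the test rejects less often than its nominal level. Background gives a reason to think that gestational age matters, since it places the greatest concern about Bf below 28 weeks.

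The stake is precision in a small trial whose sample size was set partly by feasibility. A second, smaller matter is that the plan does not say how two within-stratum results are to be read together. If one is significant and the other is not, a reader may infer a gestational-age effect that the data do not show.

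**Working it through.** **Inputs from the plan.** Effect 22.1 - 15.9 = 6.2 nM; common SD 8.5 nM; 31 per arm (calculation) or 32 per arm (planned); alpha 0.05. Two-sided testing is inferred, because power is given in both directions and a two-sided test reproduces the figure.

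**The plan's own figure.** At 32 per arm, SE = 8.5 × sqrt(2/32) = 2.125 and the noncentrality is 6.2/2.125 = 2.92. The noncentral t distribution gives power 0.807 at 31 per arm and 0.819 at 32. The stated 0.81 is reproduced.

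**Assumptions.** The plan gives no Bf by stratum. Let D be the difference in mean Bf between strata and p the share of infants in one stratum. Total SD is held at 8.5, the effect is 6.2 nM in both strata, Bf is normal, and all 64 infants contribute. Then

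- within-stratum SD = sqrt(8.5² - p(1-p)D²)
- adjusted SE = within-stratum SD × sqrt(2/32), with 64 - 3 = 61 df

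Example with D = 6 and p = 0.5: sqrt(72.25 - 9) = 7.95, so the adjusted SE is 1.988 against 2.125 unadjusted.

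**Allocation balanced within equal strata** (simulation, 200,000 trials per setting):

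| D (nM) | Share of variance | Power, unadjusted | Power, adjusted | Unadjusted interval wider by | Type I error, unadjusted |
|---|---|---|---|---|---|
| 0 | 0% | 0.818 | 0.818 | 0% | 0.050 |
| 2 | 1% | 0.821 | 0.825 | 0.7% | 0.049 |
| 4 | 6% | 0.825 | 0.840 | 3% | 0.043 |
| 6 | 12% | 0.833 | 0.866 | 7% | 0.036 |
| 8 | 22% | 0.846 | 0.903 | 14% | 0.026 |

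The noncentral t distribution with 61 df gives adjusted power of 0.819, 0.824, 0.840, 0.866 and 0.902, which agrees. The mean 95% half-width at D = 8 is 4.25 nM unadjusted and 3.73 nM adjusted. With a 25:75 split, the interval is 0% to 10% wider and the gain in power is 0 to 0.043.

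**Allocation not stratified.** The unadjusted test keeps its size (0.049 to 0.051 with equal strata). For D = 0, 2, 4, 6 and 8, adjustment changes power by -0.007, -0.002, +0.014, +0.043 and +0.080 with equal strata, and by -0.006, -0.003, +0.010, +0.030 and +0.058 with a 25:75 split. The break-even gap is roughly 2 to 4 nM. The adjusted test has size 0.049 to 0.051 in every setting.

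**Within-stratum tests.** If the two tests have power q1 and q2, the chance that exactly one is significant is q1(1-q2) + q2(1-q1).

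- Equal strata, 16 per arm in each, D = 0: q1 = q2 = 0.515, giving 2 × 0.515 × 0.485 = 0.50. Over D = 0 to 8 the range is 0.47 to 0.50.
- 25:75 split, 8 and 24 per arm, D = 0: 0.275 × 0.304 + 0.696 × 0.725 = 0.588. Over D = 0 to 8 the range is 0.59 to 0.60.

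**Arm-by-stratum difference.** With equal strata and D = 0, SE = 8.5 × sqrt(4/16) = 4.25 and the 95% half-width (60 df) is 8.5 nM. Across all settings it runs from 7.5 to 9.8 nM.

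**The case against.** The strongest reply is that nothing here is broken. The t test is valid and unbiased, its type I error is not inflated, and it matches the comparison on which the sample size was based. All of that stands. The gain also depends on a gap that the plan does not state: at 2 nM it is 0.003 in power, at 4 nM it is 0.015, and the largest balanced gain (0.057) needs a gap of 8 nM, about half the assumed Intralipid mean of 15.9 nM. If allocation is not stratified, adjustment loses a little at small gaps. This limits the size of the point but does not remove it, since the worst loss is about 0.007 and the gain can be ten times that.

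On the secondary point, the plan nowhere says that a split in significance will be read as a gestational-age effect. Estimates below 28 weeks are of interest in their own right, and the promised intervals supply what is needed for the contrast. That is fair. What remains is that the plan gives no reading rule, and the contrast would be too imprecise to settle much: its half-width exceeds the 6.2 nM effect.

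Finally, a model with arm and stratum must say which Bf value it uses. The primary outcome covers the first and second day at 3 g/kg/day, while the sample-size hypothesis refers to day 2. The planned t test has the same ambiguity, but replacement wording should not carry it forward.

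**Conclusion.** The concern holds as a matter of efficiency, not validity. The plan treats gestational age as a stratification factor and then leaves it out of the one comparison that answers the hypothesis. Under balanced allocation with equal strata, gaps of 0 to 8 nM mean an interval up to 14% too wide and up to 0.06 of power forgone. At a gap near the treatment effect (6 nM), the figures are 7% and 0.033. If the strata have similar Bf, there is nothing to gain and almost nothing to lose. These sizes rest on assumed gaps and stratum shares, a total SD of 8.5 nM, and full data on 64 infants. The sample size and stated power need no correction.

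**What to change.** Replace the overall t test for mean Bf with wording such as: *Mean Bf will be compared between arms over all patients with a linear model containing arm and gestational-age stratum (<28 versus ≥28 weeks), using one Bf value per infant; the adjusted difference and its 95% confidence interval will be reported.* State which value that is: day 1, day 2 or their average. If both days enter as separate records, the model must allow for correlation within infants.

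Label the within-stratum comparisons descriptive. Report the arm-by-stratum difference with its 95% interval as exploratory, and say that it is imprecise. State in Methods whether the REDCap allocation is stratified at 28 weeks.

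The cost is analysis wording and one degree of freedom. The only extra variable is gestational age, known at enrolment. If the strata do not differ, power is unchanged under balanced allocation and falls by about 0.007 at most under unstratified allocation.

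### The only gestational-age analysis is a separate t test in each stratum, which does not test whether the emulsion effect differs by gestation and, at the planned effect, gives conflicting stratum results in about half of trials or more

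*Combined protocol and SAP*

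**What the plan says.** The Data Analysis section has means compared by Student's t test "over all patients and within gestational age strata". The strata come from Study Population, where infants under 32 weeks are "stratified <28 weeks versus ≥ 28 weeks". The expected number in each stratum is not given.

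Data Analysis assigns multilevel regression to dose response with repeated measures and promises point estimates with 95% intervals for all outcomes. It names no arm-by-stratum interaction, gives no rule for reading stratum results that disagree, and does not say whether the stratum tests are confirmatory or descriptive.

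The Hypothesis is a single overall contrast at 3 g/kg/day. Power and Sample Size likewise covers only that contrast: "a feasible sample size of 64 patients (32 in 2 groups) would result in power of 0.81 with alpha at 0.05", supported by a calculation in which "a sample size of 62 patients (31 in 2 groups) will result in power of 0.81 with alpha at 0.05". The Background gives the reason for interest in the youngest infants: lipid infusion might raise free bilirubin to dangerous levels, "particularly in newborns delivered at <28 weeks gestational age".

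**The concern.** A significant result in one stratum beside a non-significant result in the other is not evidence that the effects differ. That question needs an estimate of the difference between the two stratum effects, with its own standard error. The plan does not provide one.

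The Background singles out infants below 28 weeks, and the strata are cut at that point. The below-28-week p value is therefore likely to be read as the answer for those infants and compared with the p value in the older stratum. If the effect were the same in both strata, a non-significant result in the younger one could be taken as reassurance that the data do not give. A significant result there alone could be taken as a special hazard that the data do not show.

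**Working it through.** **Inputs from Power and Sample Size.** Bf means are 15.9 nM (IL) and 22.1 nM (SMOF), so the difference is 22.1 − 15.9 = 6.2 nM (39%). The SD is 8.5 nM, alpha is 0.05, and 32 per arm are planned. Sidedness is not stated in words. Two-sided is implied, because power is also given for the opposite direction: "Likewise, power will be 0.81 to detect an 39% decrease (SMOF 9.7 ± 8.5".

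**Assumptions.** The stratum split is not in the documents, so I take a range from 16/16 to 8/24 infants per arm. The SD of 8.5 is applied within each stratum, and all 64 infants are taken as evaluable.

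**1. The plan's own figure.** For a two-sided two-sample t test, the noncentrality is 6.2 / (8.5·√(2/n)), with 2n − 2 degrees of freedom.
- n = 31 per arm: noncentrality 2.87, power 0.807.
- n = 32 per arm: noncentrality 2.92, power 0.819.

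The stated 0.81 is reproduced for the overall comparison.

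**2. Power within strata, same effect in both.** The formula is the same, with n the number per arm in the stratum. With stratum powers p and q, the chance that exactly one stratum is significant is p(1 − q) + q(1 − p).

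| Per-arm split | Power, first stratum | Power, second stratum | Exactly one significant |
|---|---|---|---|
| 16/16 | 0.515 | 0.515 | 50% |
| 12/20 | 0.401 | 0.613 | 52% |
| 11/21 | 0.370 | 0.636 | 54% |
| 8/24 | 0.275 | 0.696 | 59% |

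For 16/16: 0.515 × 0.485 + 0.515 × 0.485 = 0.50. Both strata are significant in 26.5% of trials and neither in 23.5%. Simulation of 200,000 trials agrees (49.8%).

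**3. Dependence on the true effect (16/16).** Discordance for other common effects:

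| Common effect (nM) | 0 | 3 | 4 | 5 | 6.2 | 8 | 10 |
|---|---|---|---|---|---|---|---|
| Exactly one significant | 9.5% | 27% | 38% | 46% | 50% | 39% | 19% |

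**4. Three tests with no effect.** In simulation, the chance that at least one of the overall and two stratum tests has p<0.05 is about 0.116 at 16/16 and 0.113 at 11/21. It is below 1 − 0.95³ = 0.143 because the overall test shares its data with the stratum tests.

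**5. What an interaction analysis would deliver.** The SE of the difference between stratum effects is 8.5·√(2/n₁ + 2/n₂), where n₁ and n₂ are the per-arm stratum sizes. The 95% half-width uses t with 60 degrees of freedom (2.00).
- 16/16: SE = 8.5·√(0.125 + 0.125) = 4.25, half-width ±8.5 nM.
- 11/21: SE = 4.47, half-width ±8.9 nM.
- 8/24: SE = 4.91, half-width ±9.8 nM.

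When the effects are equal, the interaction test gives a false signal in 5% of trials (simulated 4.9% to 5.0%). At 16/16 its power to detect a 6.2 nM difference between strata is only about 0.31, and the difference detectable with 80% power is about 11.9 nM (normal approximation).

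**The case against.** The strongest reply is that the plan never sets out to show effect modification. Its hypothesis and power calculation concern one overall contrast, and a t test within a stratum is a valid answer to a different question: what is the difference among these infants? The Background remark is about absolute risk from lipid and does not say that the SMOF–Intralipid difference depends on gestation. This stands, so the point is a gap in a secondary analysis.

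A reader might infer that the stratum tests will disagree half the time whatever the truth. The documents do not support that. The rate holds near 6.2 nM, and that effect is carried over from triglycerides for want of other data. A reader might also infer that the trial's stated error rate is more than doubled. The plan states no family-wise rate, gives alpha 0.05 only for the overall comparison, and that test keeps its own error rate.

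The promised 95% intervals, if they extend to the strata, would let a careful reader work out the difference between them. That softens the problem without removing it, because separate intervals give no direct interval or test for the difference, and nothing labels the stratum results as descriptive.

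Finally, the interaction is poorly powered. That is a reason to report it as an estimate with an interval. The wide interval shows what 64 infants cannot resolve, which a pair of stratum p values hides.

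**Conclusion.** The point holds as a weakness in the secondary stratum analysis and should be corrected. At the planned effect, and over the assumed splits, stratum power is about 0.27 to 0.70, and identical true effects give one significant and one non-significant stratum in about 50% to 59% of trials. With no effect, about 12% of trials have p<0.05 in at least one of the three tests.

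These figures rest on the plan's 6.2 nM and SD 8.5, on an SD that is the same in each stratum, on complete data, and on a split that the documents do not give. Missing samples would lower stratum power slightly (15 per arm: 0.488) and leave discordance near half. A smaller SD within strata would raise stratum power.

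A reader might go further and infer that the trial's main result is compromised. It is not: the overall comparison, its sample size and its data collection are untouched.

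**What to change.** In Data Analysis, replace the within-stratum t tests by one linear model for Bf with terms for arm, stratum and arm-by-stratum. State that:

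- the interaction estimate is reported with its 95% CI as exploratory, because power is low;
- the stratum-specific differences, with CIs from the same model, are descriptive;
- only the overall comparison is tested at 0.05, and a difference by gestation is claimed only on the interaction.

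The cost is a few sentences, with no extra patients, samples or data. The downside is that the trial can no longer report a stand-alone significant result for one stratum.
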